#### 16.2.4.2 ANOVA Model Pairwise Comparisons

Following log-e transformation, dose-normalized PK parameters will be analyzed with an ANOVA model using PROC MIXED. Each dose will be compared with a reference dose on a pair-wise basis. Pairwise

comparisons of the ratio of GLS means and the corresponding 90% CI will be estimated for each PK parameter of interest. Although there is no formal statistical hypothesis tested for this secondary objective, if the 90% CI for the geometric LSM ratio falls completely within the 0.8 to 1.25 equivalence region then dose proportionality is indicated for the specific comparison. No adjustment for multiplicity will be performed for the set of descriptive pairwise comparisons.

The SAS PROC MIXED pseudo code for the pairwise comparison for the ANOVA model is as follows:

```
data adpp;
set adpp;
ln_auc_dose = log(auc)/dose;
run;

ods output diffs=diffs;
ods output lsmeans=lsmeans;
proc mixed data=adpp method=reml;
by parameter;
class dose;
model ln_auc_dose = dose / ddfm=kr;
lsmeans dose / pdiff alpha=0.1 cl;
run;
```

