12.3.1.5.2. Analysis of Variance

Following log-e transformation, dose-normalized PK parameters will be analyzed with an ANOVA model using PROC MIXED. Each dose will be compared with a reference dose on a pair-wise basis. The ratio of GLS means and the corresponding 90% CI will be estimated for each PK parameter of interest.

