### 9.2.2 Treatment/Subject Grouping

Throughout this SAP, study drug refers to: BCX4430 galidesivir for IV infusion.

Label	Grouping
Study Drugs	BCX4430 galidesivir for IV infusion
Treatment	
Cohort 1:
 
 
Regimen A: Galidesivir (Dose 5 mg/kg, Calculated Dose Range 250-500 mg, Concentration 1.0 mg/mL, Dose Volume 250-500 mL), or
 
Placebo (Dose Volume 250-500 mL)
 
 
Cohort 2:
 
 
Regimen B: Galidesivir (Dose 10 mg/kg, Calculated Dose Range 500-1000 mg, Concentration 1.0-2.0 mg/mL, Dose Volume 500 mL), or
 
Placebo (Dose Volume 500 mL)
 
 
Cohort 3:
 
 
Regimen C: Galidesivir (Dose 15 mg/kg, Calculated Dose Range 750-1500 mg, Concentration 1.5-3.0 mg/mL, Dose Volume 500 mL), or
 
Placebo (Dose Volume 500 mL)
 
 
Cohort 4:
 
 
Regimen D: Galidesivir (Dose 20 mg/kg, Calculated Dose Range 1000-2000 mg, Concentration 2.0-4.0 mg/mL, Dose Volume 500 mL), or
 
Placebo (Dose Volume 500 mL)
 

Dose Levels	
BCX4430: 5 mg/kg, Calculated Dose Range 250-500 mg
 
BCX4430: 10 mg/kg, Calculated Dose Range 500-1000 mg
 
BCX4430: 15 mg/kg, Calculated Dose Range 750-1500 mg
 
BCX4430: 20 mg/kg, Calculated Dose Range 1000-2000 mg
 
[Note: Treatment labels will use mg/kg]

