#### 9.4.3.2 Secondary Objective – Dose Proportionality

Dose proportionality for  $AUC_{inf}$ ,  $AUC_t$ , and  $C_{max}$  will be evaluated using the power model (including all doses) and also using an ANOVA model where each dose will be compared with a reference dose in a pairwise basis. The mean slope from the power model and the set of pairwise comparisons from the ANOVA method will constitute descriptive evaluations of dose proportionality.

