**Analysis of Variance**

Following log-e transformation, dose-normalized PK parameters will be analyzed with an ANOVA model using PROC MIXED. Each dose will be compared with a reference dose on a pairwise basis. The ratio of geometric least squares means (LSM) and the corresponding 90% CI will be estimated for each PK parameter of interest. If the 90% CI for the geometric LSM ratio for a given pairwise comparison falls completely within the 0.8 to 1.25 equivalence region then dose proportionality is indicated.

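### The SAP's ANOVA code for dose proportionality divides the logarithm of the parameter by dose, instead of taking the logarithm of the dose-normalised parameter

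*SAP*

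**What the plan says.** Dose proportionality of galidesivir is a secondary endpoint (Protocol 6.2, SAP 5.2.1). It is assessed by a power model and by a pairwise ANOVA on AUCinf, AUCt and Cmax.

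For the ANOVA, Protocol 12.3.1.5.2 states: "The ratio of GLS means and the corresponding 90% CI will be estimated for each PK parameter of interest". SAP 9.4.3.2 repeats this: "The ratio of geometric least squares means (LSM) and the corresponding 90% CI will be estimated for each PK parameter of interest". The response is described as follows: "Following log-e transformation, dose-normalized PK parameters will be analyzed with an ANOVA model using PROC MIXED". SAP 16.2.4.2 adds the decision rule, that if the 90% CI "falls completely within the 0.8 to 1.25 equivalence region then dose proportionality is indicated for the specific comparison". SAP 9.4.3.2 sets the status of the result: "the set of pairwise comparisons from the ANOVA method will constitute descriptive evaluations of dose proportionality".

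The only data step that SAP 16.2.4.2 gives for this analysis is "ln_auc_dose = log(auc)/dose". It feeds a PROC MIXED model with dose as a class factor, and the contrasts come from "lsmeans dose / pdiff alpha=0.1 cl". SAP 7.1 declares no changes from the protocol, so the code is not a declared change of method.

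**The concern.** Dividing a parameter by dose and then taking logs gives log(AUC) − log(dose). Differences between doses then back-transform to a ratio of dose-normalised geometric means, which equals 1 under proportionality. Taking the log and then dividing by dose gives a different quantity. Its differences do not back-transform to any ratio of dose-normalised exposures, and nothing makes them zero when exposure is proportional.

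A programmer who follows the code literally would compare a meaningless number with 0.8 to 1.25 for all three parameters. Proportional data could be reported as failing, and non-proportional data as passing, depending on the dose pair and the AUC unit. An independent QC programmer working from the same line would reproduce the same wrong output.

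**Working it through.** The documents give no expected result for this ANOVA, so there is no plan figure to reproduce. The check compares the coded response with the one the text requires.

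**Inputs.** Doses are 5, 10, 15 and 20 mg/kg with 6 active subjects each (SAP 6.0). Dose is taken in mg/kg (SAP 9.2.2: "Note: Treatment labels will use mg/kg"). Expected exposure is AUC24 of about 10,000 ng.h/mL at 5 mg/kg and about 47,000 at 20 mg/kg (Protocol 4.4.3). Interim CVs at 10 mg/kg are Cmax 10.6%, AUC0-24h 12.8%, AUC0-last 14.1% and AUC0-inf 20.9% (10 mg/kg dose escalation summary with the SAP, PK Summary). The CVs serve as assumptions. True slopes other than 1 are stress values.

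**1. Exactly proportional data.** AUC is 10,000, 20,000, 30,000 and 40,000 ng.h/mL. As coded, y = ln(AUC)/dose:

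- 5 mg/kg: 9.2103/5 = 1.8421
- 10 mg/kg: 9.9035/10 = 0.9903
- 15 mg/kg: 10.3090/15 = 0.6873
- 20 mg/kg: 10.5966/20 = 0.5298

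Exponentiated differences, for example exp(0.9903 − 1.8421) = 0.43:

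| Pair | Correct | As coded, ng.h/mL | As coded, µg.h/mL |
|---|---|---|---|
| 10 v 5 | 1.00 | 0.43 | 0.85 |
| 15 v 5 | 1.00 | 0.31 | 0.79 |
| 20 v 5 | 1.00 | 0.27 | 0.76 |
| 15 v 10 | 1.00 | 0.74 | 0.93 |
| 20 v 10 | 1.00 | 0.63 | 0.89 |
| 20 v 15 | 1.00 | 0.85 | 0.96 |

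**2. Unit dependence.** Rescaling AUC by c adds ln(c)/dose to each group, and this does not cancel between doses. From ng to µg, ln(0.001) = −6.908. The 10 v 5 difference therefore shifts by −0.691 + 1.382 = +0.691, and 0.427 × e^0.691 = 0.85. With log(AUC/dose) the shift is ln(c) in every group and cancels.

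**3. Response to the slope.** With AUC = A(dose/5)^β, the coefficient of β in a coded difference is ln(d1/5)/d1 − ln(d2/5)/d2. For 20 v 10 this is ln4/20 − ln2/10 = 0, so with A fixed that ratio is the same whatever the slope. For 20 v 15 it is 0.0693 − 0.0732 = −0.004, and the ratio moves only from 0.856 (β = 0.5) to 0.851 (β = 2).

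**4. The protocol's own expected exposures, 20 v 5 mg/kg.** Correct: (47,000/20)/(10,000/5) = 2,350/2,000 = 1.175. As coded: exp(10.7579/20 − 9.2103/5) = exp(0.5379 − 1.8421) = 0.27. A modestly more-than-proportional rise appears as a large shortfall.

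**5. Variance.** With σ the SD of ln(AUC), the coded residual SD is σ/dose, four times larger at 5 than at 20 mg/kg. The pooled variance is σ²(1/25 + 1/100 + 1/225 + 1/400)/4 = 0.01424σ². Model SE relative to true SE is √(2 × 0.01424/(1/25 + 1/100)) = 0.75 for 10 v 5, and √(2 × 0.01424/(1/225 + 1/400)) = 2.0 for 20 v 15.

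**6. Simulation.** 20,000 trials per setting, lognormal data, pooled-variance ANOVA with 20 df; a pass means the 90% CI lies within 0.8 to 1.25.

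- As coded in ng.h/mL, true slope 1: five pairs pass in 0% of trials and 20 v 15 in 100%, at every CV from 10.6% to 20.9%.
- 20 v 15 also passes in 100% at true slope 0.5 or 2 (CV 12.8%); correct code passes it in about 27% and 1%.
- As coded in µg.h/mL, true slope 1, CV 12.8%: four of six pairs pass in 100%, 15 v 5 in about 1% and 20 v 5 in 0%.
- Correct code, true slope 1: each pair passes in about 94%, 80%, 69% and 16% at CV 10.6%, 12.8%, 14.1% and 20.9%.
- As coded, the nominal 90% CI covers its own target in about 78–81% of trials for pairs with 5 mg/kg and 96–99.5% for the others.

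**7. Other anchors.** Half the interim 10 mg/kg geometric means (assuming proportionality) gives the same pattern. AUCinf 16,200 gives 0.41, 0.30, 0.25, 0.73, 0.62, 0.85. Cmax 4,620 gives 0.46, 0.35, 0.30, 0.76, 0.66, 0.87.

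**The case against.** The SAP labels this as pseudo code, the surrounding text describes the right estimand, and the production program is not visible. Outputs are QC'd and go to the sponsor in draft, where a ratio of 0.27 beside a power-model slope near 1 should be noticed. This mitigates the risk. But it is the only data step given for the analysis, and nothing says that QC would check against the text rather than the code.

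The text could be read literally as log first, then divide. That reading cannot yield the geometric mean ratio that the same text asks for.

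The false-pass case is narrow in ng.h/mL, the unit the documents use: only 20 v 15 passes. The text compares each dose with a reference dose that it does not name. If that is 5 mg/kg, the error can only falsely fail, although the code as given outputs all pairs. The protocol's expected exposures imply a slope of ln4.7/ln4 = 1.12, so the realistic harm is failing near-proportional data. These points stand.

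Three interim Cmax values exceeded the assay's upper limit and were not re-assayed, so the 10.6% CV and the Cmax mean may be too low and the 94% pass rate optimistic. This also stands, but does not alter the as-coded results.

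If dose were held in mg (75 kg subjects, an assumption), the coded ratios would be about 0.98 to 1.00 whatever the slope, so nearly everything would pass. The same variable is the class factor, however, and individual mg doses would not form four groups. In either unit the line is wrong.

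**Conclusion.** The line is wrong as written and should be corrected before the analysis is programmed. With dose in mg/kg and AUC in ng.h/mL, exactly proportional exposure would be reported with ratios of 0.27 to 0.85 instead of 1.00. Five of six pairs would always fail the rule, and the sixth would always pass across the slopes tested. The algebra and the unit dependence are exact. The ratios depend on the assumed exposure level and on mg/kg coding. The pass rates also depend on interim CVs and assumed slopes, and the correct-code rate for Cmax is probably optimistic.

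The reach is limited to one of two descriptive analyses of a secondary endpoint. The power-model code in SAP 16.2.4.1 does not contain this error, and neither the safety analyses nor any escalation decision depends on it.

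**What to change.** In SAP 16.2.4.2, replace the line with `ln_auc_dose = log(auc/dose)`, equivalently `log(auc) - log(dose)`. The existing BY statement applies it to AUCt, AUCinf and Cmax. Add that the least squares mean differences and their 90% limits are exponentiated before comparison with 0.8 to 1.25.

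Optionally, reword the method sentence in SAP 9.4.3.2 and 16.2.4.2 to say that parameters are divided by dose and then log-e transformed.

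The cost is one line of code and a sentence or two, with no change to design or data collection.

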## 17.0 Safety Analyses

The safety summaries described in this section will be created using the safety analysis population. Safety analyses will be performed separately for each cohort.

### 17.1 Safety Variables

The following safety variables will be included:

- Adverse events
- Clinical laboratory evaluations
  - Cardiac markers (troponin and creatine kinase-MB [CK-MB])
  - Chemistry
  - Coagulation
  - Hematology
  - Urinalysis
  - Serology
  - Pregnancy
  - Alcohol breath test and urine drug screen
- Vital signs
  - Systolic blood pressure
  - Diastolic blood pressure
  - Pulse rate
  - Oral body temperature
- Electrocardiograms
  - Heart rate
  - RR interval
  - PR interval
  - QRS duration
  - QT interval
  - QT interval corrected using Fredericia's method (QTcF)
- Physical examination findings

### 17.1.1 Adverse Events

An AE is defined as any new untoward medical occurrence or worsening of a preexisting medical condition in a clinical investigation participant that does not necessarily have a causal relationship with treatment. TEAEs are those which occur during or after the administration of the first dose of study drug. All TEAE summaries will be presented alphabetically by system organ class, with preferred terms sorted in decreasing order of frequency within each system organ class based on MedDRA Version 21.1.

The following missing data will be imputed (for calculations only) as defined:

- Missing AE start and / or end times for the calculation of onset and duration will be assumed to be at 00:01 for a start time and 23:59 for end times
- Missing AE severity or relationship will be assumed to be severe or related, respectively
- Missing AE start times for the determination of treatment emergence will be assumed to occur after treatment unless partial date documents the AE as happening prior to treatment
- Missing AE start times for the determination of treatment assignment will be assumed to occur after treatment on the recorded date 1 minute after dosing
- Missing AE start date will be assumed to be after treatment for the determination of TEAE but will not be attributed to a specific study drug

A summary of the number and percentage of subjects reporting AEs, TEAEs, serious AEs (SAEs), and who discontinued study drug due to an AE will be provided by cohort and overall for the study.

A summary of the number and percentage of subjects reporting each TEAE will be provided by cohort and treatment, and overall. Counting will be done by subject, not by event; subjects will only be counted once within each system organ class or preferred term.

A summary of the number and percentage of subjects reporting each TEAE will be provided by relationship to treatment (BCX4430 formulation, as recorded on eCRF) and by cohort and treatment, and overall. Subjects with multiple events will be counted under the category of their most-related event within each system organ class or preferred term.

A summary of the number and percentage of subjects reporting each TEAE will be provided by severity (as recorded on eCRF) and by cohort and treatment, and overall within each cohort. Subjects with multiple events will be counted under the category of their most severe event within each system organ class or preferred term.

All AEs (including non-treatment-emergent AEs) recorded on the eCRF will be listed by subject.

A separate listing of AEs leading to study drug discontinuation will be provided by subject.

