## 6.0 Study Design

[figure not shown]
This SAD study will evaluate the safety, tolerability, and PK of single doses of galidesivir vs. placebo administered as IV infusions in healthy subjects enrolled in up to four dose cohorts of 8 subjects each, for a total of 32 subjects. A single dose of study drug will be administered per cohort: 6 subjects will receive galidesivir IV, and 2 subjects will receive matching placebo.

The planned cohorts are as follows:

- Cohort 1, Regimen A: 5 mg/kg galidesivir or placebo, IV infusion × 1 dose
- Cohort 2, Regimen B: 10 mg/kg galidesivir or placebo, IV infusion × 1 dose
- Cohort 3, Regimen C: 15 mg/kg galidesivir or placebo, IV infusion × 1 dose
- Cohort 4, Regimen D: 20 mg/kg galidesivir or placebo, IV infusion × 1 dose

Subjects will be randomized within each cohort to receive either galidesivir or placebo. As a safety precaution, on the first day of dosing in each cohort, only 2 subjects will be dosed (to be referred to as sentinel subjects). The randomization schedule will be constructed such that 1 of the sentinel subjects dosed on the first day will be randomized to receive galidesivir and 1 will be randomized to receive placebo. After review of the safety data from the 24-hour post-dose period for the sentinel subjects, which includes review of any AEs, any abnormalities in the bedside ECGs, safety laboratory assessments and vital signs, the remainder of the cohort (5 subjects randomized to galidesivir; 1 randomized to placebo) will be dosed at least 2 days after the sentinel subjects.

Enrollment of subjects in each sequential higher dose level cohort will occur only after completion of a clinical safety review of laboratory, AE, vital sign, ECG (12-lead and telemetry), and PE data for all subjects up through 96 hours post-dose and plasma PK data through 24 hours post-dose. Based upon safety review and evaluation of the data for each subject, adjustments in the dose escalation scheme for the next cohort may be made, including omission of higher dose cohorts in the event that the safety and PK parameters have been adequately characterized with lower dose cohorts. Where considered appropriate to meet the study objectives, adjustments in the protocol-specified dose escalation for subsequent cohorts are permissible (i.e., an intermediate dose between the previous tolerable dose and the scheduled next higher dose). The study design is shown in Figure 1 (below).

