### 9.2.3 Common Variable Derivations

Variable	Data Type	Definition/Calculation
Change from baseline	All	Post-dose observation minus baseline observation
Analysis study day (prior to dose)	All	Date of measurement minus dose date
Analysis study day (post dose)	All	Date of measurement minus dose date + 1
TEAE	AE	An AE is a treatment-emergent adverse event (TEAE) if the AE start date/time is greater than or equal to the first dose date/time

Abbreviations: AE = adverse event; TEAE = treatment-emergent adverse event.

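### SAP 17.1.1 counts an AE with no start date as treatment-emergent but attributes it to no study drug, although each subject receives only one treatment

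*SAP*

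**What the plan says.** SAP 17.1.1 lists rules for missing AE data. Those that matter here are:

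- **Missing start date.** The event "will be assumed to be after treatment for the determination of TEAE but will not be attributed to a specific study drug".
- **Missing start or end time, for onset and duration.** Times "will be assumed to be at 00:01 for a start time and 23:59 for end times".
- **Missing start time, for treatment emergence.** The event "will be assumed to occur after treatment unless partial date documents the AE as happening prior to treatment".
- **Missing start time, for treatment assignment.** The event "will be assumed to occur after treatment on the recorded date 1 minute after dosing".
- **Missing severity or relationship.** Taken as severe and as related.

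SAP 9.2.3 separately derives an AE as a TEAE "if the AE start date/time is greater than or equal to the first dose date/time".

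On the design, SAP 6.0 states: "A single dose of study drug will be administered per cohort", with 6 subjects on galidesivir and 2 on placebo in each cohort. SAP 10.1 analyzes the safety population by treatment received, and SAP 9.1.4 pools placebo subjects in summary outputs. SAP 17.1.1 tabulates TEAEs by cohort and treatment and overall, counting each subject once within a system organ class or preferred term. Protocol 12.3.1.3 likewise summarizes TEAEs by cohort and treatment assignment, treats an untimed Day 1 AE as treatment-emergent, and makes no exception for undated events.

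**The concern.** Leaving an undated event unattributed makes sense in a crossover or multi-period study, where the date decides which treatment the subject was on. Here there is nothing to decide. The SAP nonetheless tells the programmer to accept the event as a TEAE and then withhold it from any study drug, and it defines no column for unattributed events. AEs are part of the primary endpoint and the columns are small, so one misplaced subject would be visible. A column and the overall total could also fail to reconcile.

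The time rules raise a smaller problem of the same kind. The same untimed Day 1 event is placed after dosing for emergence and assignment, but just after midnight for onset. A TEAE can therefore carry an onset earlier than the infusion.

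**Working it through.** The plan gives no figure on this point, so there is none to reproduce. The check applies the rules as written.

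**1. Is the treatment ever unknown?** Each subject has one treatment on one occasion (SAP 6.0), the safety population contains only dosed subjects, and treatment received is the analysis variable (SAP 10.1). The column is fixed by the subject and does not depend on the AE date.

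**2. Size of a misplaced undated event.** Planned numbers are 4 cohorts of 6 galidesivir + 2 placebo subjects. Percentages use the number exposed within a treatment (SAP 9.1.3), and placebo is pooled (SAP 9.1.4).

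| Column | n | One subject |
|---|---|---|
| One dose level | 6 | 1/6 = 16.7 points |
| Pooled placebo | 4 × 2 = 8 | 1/8 = 12.5 points |
| Overall | 4 × (6 + 2) = 32 | 1/32 = 3.1 points |

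Suppose one subject in a dose group of 6 has a single, undated event in a given term and no one else in the group has that term. Under the literal rule the dose column shows 0/6 when it should show 1/6, while the overall column still counts the subject. If the same subject also has a dated TEAE in that term, the dose column shows 1/6 either way, because counting is by subject. The change is then zero.

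**3. Direction.** Omitting a galidesivir subject lowers that dose's incidence and narrows the difference from placebo. Omitting a placebo subject lowers the placebo incidence and widens the difference.

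**4. Missing Day 1 start time.** Protocol 9.13 puts dosing on the morning of Day 1, one hour after breakfast, without a clock time. I assume 07:00 to 11:00.

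- Onset with 00:01: 00:01 − 07:00 = −6 h 59 min = −6.98 h. For an 11:00 dose it is −10 h 59 min = −10.98 h. Any dose given after 00:01 yields a negative value.
- Onset with dose time + 1 minute: 1/60 = +0.02 h, whatever the dose time.
- Duration if the end time is also missing on the same day: 23:59 − 00:01 = 23.97 h. Starting at dose time + 1 minute it would be 23:59 − 07:01 = 16.97 h, down to 23:59 − 11:01 = 12.97 h.
- Putting 00:01 into the SAP 9.2.3 derivation would return not a TEAE. The separate emergence rule in SAP 17.1.1 prevents that result.

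**5. Where onset or duration would appear.** The AE summaries in SAP Appendix 3 are Tables 14.3.1.1 to 14.3.1.4: overall, by system organ class and preferred term, by relationship, and by severity. None reports onset or duration.

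**The case against.** The best defence is that SAP 17.1.1 does not say the event leaves the tables. It says only that the event is not tied to a specific study drug, a term that SAP 9.2.2 defines as galidesivir. Because SAP 10.1 analyzes subjects as treated and counting is by subject, a programmer could place the event in the subject's own column without further instruction. The table shells are in a separate document, so the intended columns cannot be checked. This stands as a possible reading, and it means that loss from a treatment column is not certain. It does not remove a sentence that points the other way, and the SAP does not say which governs.

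A missing date should also be uncommon. Subjects are confined for 96 hours, AEs are reviewed at each later visit (Protocol 10.1.2 and 10.1.3), data entry has internal checks, and all AEs are listed by subject. That stands too, and it limits the point to a minor one.

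A reader might infer several stronger things that the documents do not support:

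- **That the rule can only under-count in a non-conservative direction.** A placebo omission works the other way. AEs are also collected from consent (Protocol 11.4), so presuming an undated event to be treatment-emergent can add pre-dose events to the overall count.
- **That every undated event shifts a column by 16.7 or 12.5 points.** These are ceilings, because each subject is counted once per term.
- **That the 00:01 rule strips events of TEAE status or distorts a primary-endpoint table.** Emergence and assignment have their own rules, consistent with Protocol 12.3.1.3, and no onset or duration summary is planned. For duration, 00:01 to 23:59 is a defensible longest-case convention.
- **That the rules were carried over from a multi-treatment template.** References to treatment periods in SAP 9.2.1, 17.1.4 and 17.1.5 make this plausible, but it concerns where the text came from and is not itself a defect.

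**Conclusion.** The point holds as a minor internal contradiction. One sentence in SAP 17.1.1 withholds attribution from events whose treatment is always known, contrary to SAP 10.1 and to the layout of the TEAE tables. Followed literally, it leaves a TEAE in the overall count and in no treatment column.

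The effect of one such event is at most 16.7 points in a dose group or 12.5 points in pooled placebo. It is zero if the subject has another TEAE in the same term, and its direction depends on the arm. These sizes assume full planned enrolment with 6 dosed per dose level and placebo pooled across four cohorts. The documents give no rate of missing dates; I take it to be low.

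The pre-dose onset for an untimed Day 1 TEAE is a consistency matter only. Its sign holds for any morning dose, its size rests on the assumed dosing hours, and it reaches nothing beyond derived values in listings or datasets.

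**What to change.** Replace the missing-start-date rule in SAP 17.1.1 with: *AEs with a missing start date are TEAEs, unless a partial date or stop date shows that they preceded dosing, and are attributed to the treatment the subject received.* The exception is needed because AE collection begins at consent, and it matches the partial-date exception that the SAP already makes for missing times.

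As a consistency edit, state that for a Day 1 TEAE with a missing start time, derived onset uses dose time + 1 minute in place of 00:01. If 00:01 is kept for duration, say that this is deliberate.

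The cost is two sentences in the SAP and the matching lines in the AE dataset specification. No new data, tables or analyses are needed.
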